2.2 FACT-P

The FACT-P will be used to assess health-related quality of life and prostate cancer-specific symptoms. The FACT-P consists of the 27-item FACT-General (FACT-G) and 12 items for the prostate cancer specific concerns. Scoring guidelines for the FACT-P and handling of missing items (as opposed to missing assessments) will be in accordance with methodology described in the Manual of the Functional Assessment of Chronic Illness Therapy (FACIT) Measurement System, version 4.0 (November 1997). See Appendix 1. The scales from the FACT-P are composed of the following items, all with higher scores indicating better functioning:

- Physical Well-Being (PWB): items GP1-GP7 (scale values range from 0 to 28),
- Social/Family Well-Being (SFWB): items GS1-GS7 (scale values range from 0 to 28),

ARN-509-003	
PRO Statistical Analysis Plan v2.0 26 June 2017	Page 4 of 17

- Emotional Well-Being (EWB): items GE1-GE6 (scale values range from 0 to 24),
- Functional Well-Being (FWB): items GF1-GF7 (scale values range from 0 to 28),
- FACT-G: items from the PWB, SFWB, EWB, and FWB (scale values range from 0 to 108),
- FACT-P Prostate Cancer Subscale (PCS): the 12 items from the additional concerns section (scale values range from 0 to 48),
- FACT-P Trial Outcome Index (TOI): PWB, FWB, and PCS scales (scale values range from 0 to 104),
- FACT-P Total: scales FACT-G and PCS (scale values range from 0 to 156),
- FACT-P Pain-related Scale: Items P1-P3, and GP4 (scale values range from 0 to 16),
- FAPSI-8: pain (3 items), fatigue, weight loss, urinary difficulties (2 items), and concern about the condition becoming worse (scale values range from 0 to 32).

2.3 EQ-5D-3L

The EQ-5D-3L is a validated and reliable self-administered instrument used to assess health status. The EQ-5D-3L can be completed in less than 5 minutes.

The EQ-5D-3L^{Error! Reference source not found.} quality of life instrument is a validated tool that consists of a 5-item questionnaire and a visual analogue scale (VAS). The 5-item questionnaire measures mobility, self-care, usual activities, pain/discomfort, and anxiety/depression.

2.4 PRO SCALES

The following PRO scales will be included in the analyses.

- FACT-P (See Appendix 1 for the derivation of each scale)
 - FACT-P Total
 - PCS
 - PWB
 - EWB
 - FWB
 - FACT-G
 - TOI
 - FACT-P Pain-related Scale
 - SFWB
 - FAPSI-8
- EQ-5D-3L(See Appendix 2)
 - Health State
 - EQ VAS score

ARN-509-003 PRO Statistical Analysis Plan v2.0 26 June 2017

2.5 ANALYSIS METHODS

All analysis will be performed by treatment arm. When appropriate, separate analysis may be performed during treatment phase and follow-up phase.

Based on the PRO assessment date, the associated visit will be mapped and used for analysis. For subjects with multiple records at the same visit, the closest one to the visit date will be selected as scheduled assessment, and others will be unscheduled assessments. For those with multiple records on the same assessment date, the first one by time point and sequence number will be selected as scheduled assessment. Only scheduled visits will be presented in the by-visit analysis. All assessments will be included in the time-to-event analysis.

Analysis may be stratified by stratification factors when appropriate. In this study, patients were randomized to the treatment group based on the following stratification factors:

- PSADT: > 6 months vs. ≤ 6 months
- Bone-sparing agent use: Yes vs. No
- Loco-regional disease: N0 vs. N1

In this study, subjects may receive subsequent anti-cancer therapies after discontinuing study drug. For these subjects, only PRO measurements before the initiation of subsequent therapy will be included in analysis unless otherwise stated.

2.5.1 Analysis Population

The analysis of patient reported outcomes data described in this SAP will be based on the Intent-to-Treat population as defined below.

Intent-to-Treat Population [ITT]: All eligible patients who are randomized into the study, with study drug assignments designated according to initial randomization, regardless of whether patients receive study drug or receive a different drug from that to which they were randomized to will be included in the analyses of all efficacy and clinical benefit endpoints and patient characteristics.

2.5.2 Compliance with PRO Assessment

Missing PRO assessments are calculated as the expected number of assessments for a particular visit minus the actual number of assessments received for that visit. Compliance (% received and % missing forms) will be tabulated by treatment group and overall for baseline, each scheduled visit during treatment phase and follow-up phase. Separate tables will be constructed for FACT-P and EQ-5D-3L Forms. Expected number of assessments per visit will be determined by subject-level study completion status. These tables will resemble the example in Table 1 below.

ARN-509-003 PRO Statistical Analysis Plan v2.0 26 June 2017

Page 6 of 17

Timina of	Pla	acebo (N = x	(XX)	Apa	lutamide (N =	xxx)	Total $(N = xxx)$				
Timing of	Number of Forms, n (%)			Num	ber of Forms,	n (%)	Number of Forms, n (%)				
Assessment	Expected	Received	Missing	Expected	Received	Missing	Expected	Received	Missing		
Baseline	Xxx	xx (xx x)	xx (xx.x)	Xxx	xx (xx x)	xx (xx x)	XXX	xx (xx x)	xx (xx.x)		
Cycle 2	Xxx	xx (xx x)	xx (xx.x)	Xxx	xx (xx x)	xx (xx x)	XXX	xx (xx x)	xx (xx.x)		
Cycle 3	Xxx	xx (xx x)	xx (xx.x)	Xxx	xx (xx x)	xx (xx x)	XXX	xx (xx x)	xx (xx.x)		
Cycle 4	Xxx	xx (xx x)	xx (xx.x)	Xxx	xx (xx x)	xx (xx x)	XXX	xx (xx x)	xx (xx.x)		
	Xxx	xx (xx x)	xx (xx.x)	Xxx	xx (xx x)	xx (xx x)	XXX	xx (xx x)	xx (xx.x)		
Total	Xxx	xx (xx x)	xx (xx.x)	Xxx	xx (xx x)	xx (xx x)	XXX	xx (xx x)	xx (xx.x)		
Note: Percent	Note: Percentages calculated with the number of expected forms in each group as denominator										

Table 1: Sample Table of Compliance with PRO Assessment

2.5.3 Descriptive Statistics Over Time

Descriptive statistics (number of observations, mean, standard deviation, minimum, maximum) of scores at baseline and each scheduled visit will be produced by treatment groups for each PRO scale. For these descriptive statistics, and for all analyses specified below, the scores obtained at the end of study treatment visit will be assigned to a cycle number as the next cycle that would have been completed if the subject were to have continued receiving study treatment. Separate summaries will be performed at treatment phase and follow-up phase.

For EQ-5D-3L Scores, frequency count and percentage of each reporting level (1 to 3) over Time will be provided.

2.5.4 Time to Degradation for FACT-P

Degradation/deterioration is defined based on a clinically meaningful threshold for each specific PRO scale. Table 2 summarizes the threshold values for determining a FACT-P degradation/deterioration. Time to degradation/deterioration will be defined as the time interval from randomization to the first date a patient experiences a clinically meaningful threshold change. Subjects who did not experience degradation/deterioration will be censored at their last available assessment. Assessments in both treatment and follow-up phases will be included to determine the time of event or censoring. For subjects receiving subsequent anticcancer therapy, only the assessments on or before the subsequent therapy will be included in analysis. Time to degradation/deterioration will be compared between 2 treatment groups.

Change thresholds for deterioration on the FACT-P PCS, TOI, and FACT-P Total scales are based upon an article,⁵ which provided clinically meaningful change estimates in a prostate cancer sample based upon an anchoring methodology. The FACT-G scales (PWB, SFWB, EWB, FWB, and the FACT-G) were not addressed in that article, and so the clinically meaningful change estimates for those scales are derived from an earlier article,⁶ which

ARN-509-003	
PRO Statistical Analysis Plan v2.0 26 June 2017	Page 7 of 17

reports normative values from a large sample from the general population for the FACT-G scales. Taking one half the standard deviation is equivalent to finding a 0.5 effect size. Using this distributional technique, the clinically meaningful change estimates are defined in Table 3 below.

Scale/Sub-Scale	Threshold for definition of progression/deterioration
Physical Well-Being (PWB)	3
Social/Family Well-Being (SFWB)	3
Emotional Well-Being (EWB)	3
Functional Well-Being (FWB)	3
FACT-G (General) Scale	9
Prostate Cancer Subscale (PCS)	3
Trial Outcome Index (TOI)	9
FACT-P Total Scale	10
FACT-P Pain Scale	2
FAPSI-8	3

 Table 2:
 Time to Deterioration Thresholds for FACT-P Scales

For each PRO scale, the median time to degradation will be estimated using a Kaplan-Meier method. Additionally, hazard ratio (apalutamide / placebo) and associated 95% confidence interval will be estimated by fitting Cox's proportional hazards model stratified by baseline stratification factors (PSADT, Bone-sparing agent use, and Loco-regional disease). Hazard ratio <1 favors apalutamide group. In cases where median values cannot be computed because less than 50% of subjects experienced progression/deterioration, 25th percentiles will be reported and compared instead.

2.5.5 Repeated Measures Model of PRO

For each PRO scale, repeated measures mixed effect model⁷ will be fitted to estimate the mean PRO scores at each scheduled visit during the treatment phase. In this model the dependent variable will be the PRO score change from baseline. Fixed effects for the models will include, treatment and visit number as discrete parameters, and interaction between time and treatment; subject is included as random effect. Serial correlation is assumed, and a AR(1) correlation matrix will be explored, if appropriate, to account for the correlations between repeated measures within subjects. Lsmeans of change from baseline will be plotted for each PRO scale, by visit and treatment group. T-tests will be performed to test for the differences in mean PRO scores between treatment groups at each visit.

In this repeated measure modeling, a significant amount of missing data occur during final treatment cycles due to the subjects discontinuation of the treatment, truncation will be applied for all subsequent visits at the first visit where 90% or more of the subjects are

ARN-509-003 PRO Statistical Analysis Plan v2.0 26 June 2017

Page 8 of 17

missing for any endpoint and from either arm. Once the truncation cycle is determined, this cycle will be applied across both treatment arms. To standardize the measurement points, the End-of-Treatment assessment will be parsed out to the next scheduled cycle visit after the last treatment cycle.

ARN-509-003 PRO Statistical Analysis Plan v2.0 26 June 2017

Page 9 of 17

REFERENCES

- 2. The EuroQol Group. EuroQol-a new facility for the measurement of health-related quality of life. Health Policy 1990;16:199-208.
- EQ-5D-3L User Guide. http://www.euroqol.org/fileadmin/user_upload/Documenten/PDF/Folders_Flyers/EQ-5D-3L_UserGuide_2015.pdf
- C. N. Sternberg, A. Molina, S. North, P. Mainwaring, K. Fizazi, Y. Hao, M. Rothman, D. D. Gagnon, T. Kheoh, C. M. Haqq, C. Cleeland, J. S. de Bono, H. I. Scher. Effect of abiraterone acetate on fatigue in patients with metastatic castration-resistant prostate cancer after docetaxel chemotherapy. Annals of Oncology 24(4): 1017-1025, 2013.

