5.1.2. Analysis change from baseline of QTc (Δ QTc) in apalutamide

- The change from baseline in QTc (Δ QTc) intervals at each time point will be listed for each subject and treatment. For each treatment and time point of measurement, the change from baseline in QTc intervals (Δ QTc) will be summarized using descriptive statistics (mean, SD, median, range).
- A repeated-measures mixed model will be fitted with change from baseline in QTc (ΔQTc) as the dependent variable, and treatment (Apalutamide vs. Placebo), time point of measurement, and treatment by time point of measurement interaction as fixed effects, baseline value of QTc as covariate, and subject as a random effect. Using the estimated least square means and intra-subject variance from the model, 2-sided 90% CI for mean ΔQTc of apalutamide active treatment group at each time point will be constructed. The incidence count and percentage of subjects with QTc increase >30 to ≤60 and >60 msec will be summarized for each treatment group. The incidence count and percentage by time point will also be summarized for each treatment group. Subjects with QTc increase >60 msec will be listed.
- Mean change from baseline in QTc intervals (Δ QTc) versus time profiles for both treatments will be plotted on the same graph.

5.1.3. Analysis of the difference between apalutamide and placebo in \triangle QTc ($\triangle \triangle$ QTc)

- The treatment difference in mean (SD) of ΔQTc between apalutamide and placebo will be calculated at each matched time point.
- A repeated-measures mixed model will be fitted with ΔQTc as the dependent variable, and treatment (apalutamide vs. Placebo), time point of measurement, and treatment by time point of measurement interaction as fixed effects, baseline value of QTc as covariate, and subject as a random effect. Using the estimated least square means and intra-subject variance from the model, 2-sided 90% CI for the difference in mean ΔQTc between apalutamide and placebo at each time point will be constructed.

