2. METHODS

2.1 PRO TIME AND EVENTS SCHEDULE

Patients will be required to complete two self-administered quality of life instruments: the Functional Assessment of Cancer Therapy-Prostate (FACT-P) and the Euro-QoL Group EQ-5D^{1,Error! Reference source not found.}, according to the schedule below:

Treatment Phase:

- Cycle 1 Day 1 (before dose)
- D1 C1-C6, D1 of every 2 cycles starting at C7 to C13, then D1 of every 4 cycles unless otherwise specified

Posttreatment Phase:

- End of treatment visit
- Long-term Follow-up: every 4 months up to 12 months post progression

Patients will complete the FACT-P and EQ-5D at the clinic during the Treatment Phase PRIOR to any other clinical activity. During Long-term Follow-up contact every 4 months via clinic visit or an alternative contact method per institution policy/practice up to 12 months post progression.

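### The PRO repeated-measures model of change from baseline omits the baseline score and fixes no covariance structure, which costs precision and leaves late-visit results fragile

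*SAP*

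**What the plan says.** PRO SAP section 2.5.5 specifies one model for each PRO scale over the treatment phase.

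- Outcome: "In this model the dependent variable will be the PRO score change from baseline".
- Fixed effects: "Fixed effects for the models will include, treatment and visit number as discrete parameters, and interaction between time and treatment".
- Random part: "subject is included as random effect".
- Correlation: serial correlation is assumed, and "a AR(1) correlation matrix will be explored, if appropriate". No other structure, time scale or fallback is given.
- Tests: "T-tests will be performed to test for the differences in mean PRO scores between treatment groups at each visit". No significance level is attached.
- Missing data: the section expects substantial missingness in the final cycles, and "truncation will be applied for all subsequent visits at the first visit where 90% or more of the subjects are" missing.

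PRO SAP section 2.1 sets the visits: "D1 C1-C6, D1 of every 2 cycles starting at C7 to C13, then D1 of every 4 cycles unless otherwise specified". With 28-day cycles (protocol section 5.3.4), the gaps are 4, then 8, then 16 weeks.

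Other sections handle these matters differently. PRO SAP section 2.5 leaves stratification by the randomisation factors to judgement, and section 2.5.4 requires it in the Cox models. The QT sub-study SAP has "baseline value of QTc as covariate" in section 5.1.2, and also adjusts for baseline in sections 5.1.3, 5.2 and 5.3.

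**The concern.** Subtracting baseline is not the same as adjusting for it. The change score gives baseline a coefficient of exactly 1. Regression on baseline lets the data choose the coefficient and removes the remaining noise. Randomisation protects both estimates when data are complete, but the change score is less precise unless the correlation is close to 1.

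Dropout raises a second issue. A likelihood model copes with dropout that depends on data in the model. If dropout depends on the baseline score and that score is not in the model, the protection is only partial.

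Third, the covariance is left open. When many patients have stopped, the assumed covariance determines how much is borrowed from earlier visits and what standard error is reported. Section 2.5.5 tests every scale at every visit, so an unfixed structure leaves discretion over many p-values.

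**Working it through.** The documents state no SD, correlation, power or standard error for this model, so there is no planned figure to reproduce.

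**Step 1: precision lost by omitting baseline.** Take one visit, equal score variance s² at baseline and follow-up, and correlation r.

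- Variance of a change score: 2s²(1 − r).
- Residual variance after regression on baseline: s²(1 − r²) = s²(1 − r)(1 + r).
- Ratio, adjusted to change score: (1 + r)/2. Standard-error ratio, change score to adjusted: √(2/(1 + r)).

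r is an assumption; 1,200 is the planned sample size.

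| r | (1 + r)/2 | √(2/(1 + r)) | 1,200 × (1 + r)/2 |
|---|---|---|---|
| 0.2 | 0.60 | 1.291 | 720 |
| 0.5 | 0.75 | 1.155 | 900 |
| 0.7 | 0.85 | 1.085 | 1,020 |
| 0.9 | 0.95 | 1.026 | 1,140 |

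The last column is the number of patients, analysed with baseline adjustment, that would give the same information.

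**Step 2: stratification factors.** If they explain a share R² of the variance, omitting them multiplies the standard error by 1/√(1 − R²): 1.005, 1.026 and 1.054 for assumed R² of 0.01, 0.05 and 0.10.

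**Step 3: simulation.** There were 200 replicates with no treatment effect, 800 + 400 patients, and visits at cycles 1–7, 9, 11, 13, 17, 21, 25 and 29. Assumptions: correlation with baseline falling from 0.81 to 0.44, and exponential dropout with medians of 25 and 36 months (borrowed from the MFS planning figures). All results are in baseline-SD units.

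The actual standard error of the SAP-type model (random intercept, AR(1) on visit number, no baseline) was compared with that of an unstructured model with baseline-by-visit:

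- Cycle 13: 0.061 against 0.0535, 14% larger.
- Cycle 29: 0.0795 against 0.072, 10% larger.

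Bias of the treatment difference at cycle 29 (Monte Carlo error about 0.08/√200 = 0.006):

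| Dropout depends on | SAP-type model | Plus baseline main effect | Unstructured, baseline-by-visit |
|---|---|---|---|
| nothing | −0.005 | −0.004 | −0.003 |
| baseline, both arms | 0.031 | 0.021 | 0.002 |
| baseline, placebo only | 0.108 | 0.072 | 0.001 |

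**Step 4: reported against actual standard error, dropout unrelated to scores.**

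| Model | Cycle | Reported | Actual | Type I error |
|---|---|---|---|---|
| AR(1) on visit number | 6 | 0.0534 | 0.0492 | 3% |
| AR(1) on visit number | 29 | 0.0646 | 0.0795 | 12.5% |
| AR(1) on actual time | 29 | 0.0682 | 0.0796 | 11% |

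Monte Carlo error of the type I error is about 2 points. At cycle 29 the reported value is 0.0646/0.0795 = 81% of the truth, and switching to actual time raises it only to 0.0682/0.0796 = 86%. The main cause is constant variance. Under the assumed correlations the variance of change is 2(1 − 0.70)s² = 0.60s² at cycle 6 and 2(1 − 0.44)s² = 1.12s² at cycle 29. A single pooled variance is too large early and too small late. Reported standard errors were not recorded for the unstructured model, so its type I error is not shown here.

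**The case against.** Much can be said for the plan, and several stronger readings fail.

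- **AR(1) by visit order is the planned analysis.** It is not: the text makes it conditional and exploratory and gives no time index. The defensible criticism is that the structure is not fixed in advance.
- **The stratification factors are excluded.** PRO SAP section 2.5 permits them, and the gain is about 0.5% to 5% of the standard error. The QT model in section 5.1.2 omits them too.
- **The treatment differences are biased.** Not in general. With dropout unrelated to scores, the simulated bias is nil within Monte Carlo error. The documents do not say whether dropout will follow baseline scores, and the larger figure needs that dependence in placebo alone.
- **Chance baseline imbalance goes uncorrected.** A change score does correct for it, and with r below 1 it tends to over-correct.
- **Everything makes intervals wider.** Only the baseline omission does. The covariance fault makes late intervals too narrow.
- **Unequal visit spacing is the main fault.** Step 4 shows that it contributes less than constant variance, so a week-based correlation alone would leave most of the problem.

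Stakes are also limited. PROs are listed under Other Evaluations (protocol section 3.2.3, SAP section 2.2), outside the hierarchy in SAP section 7.5.3. The PRO comparison with a stated significance level is the stratified Mantel-Haenszel test in SAP section 7.7.3. All of this stands. What it does not answer is the missing baseline covariate, for which no reason is given, or the lack of a covariance fallback in a model that keeps visits until 90% of subjects are missing.

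**Conclusion.** The point holds as an improvement to precision and pre-specification in a supportive analysis. Omitting baseline inflates the standard error of each per-visit difference by about 15.5% to 8.5% for r between 0.5 and 0.7, and by 29% to 2.6% over 0.2 to 0.9. The formula is exact for a single visit with equal variances; r is assumed throughout.

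Bias is conditional on score-dependent dropout. At cycle 29, 0.03 to 0.11 SD would be about 0.5 to 2.2 FACT-P points if the SD were 15 to 20 (assumed), against the plan's 10-point threshold. Late intervals that are too narrow are a real possibility under AR(1) with constant variance, but the 12.5% figure belongs to the simulated scenario and is not a prediction for this trial.

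A reader might infer that the trial's main conclusions are at risk. The documents do not support that: neither MFS nor any secondary endpoint uses this model.

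**What to change.** Revise PRO SAP section 2.5.5 as follows.

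1. Add the baseline score and baseline-by-visit as fixed effects. The interaction matters: in the placebo-only scenario a baseline main effect left a bias of 0.07 SD, whereas baseline-by-visit with unstructured covariance left none.
2. Add PSADT, bone-sparing agent use and nodal stage, as recorded in the IVRS, as a minor gain.
3. Use an unstructured within-subject covariance in place of the random subject effect and AR(1), not on top of them. Through cycle 29 there are 13 follow-up visits, so 13 × 14/2 = 91 covariance parameters, and sparse late visits may prevent convergence.
4. Pre-state an ordered fallback that keeps visit-specific variances and bases correlation on actual weeks.

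The cost is SAP wording only. All variables are already collected, and patients without a baseline score cannot contribute to a change-from-baseline model as it stands.

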APPENDIX 1: FACT-PROSTATE QUESTIONNAIRES AND SCORING GUIDELINE

Version 4, US English, Copyright 1987, 1997

COPYRIGHT MATERIAL

ARN-509-003 PRO Statistical Analysis Plan v2.0 26 June 2017

Page 11 of 17

COPYRIGHT MATERIAL

ARN-509-003 PRO Statistical Analysis Plan v2.0 26 June 2017

Page 12 of 17

COPYRIGHT MATERIAL

JNJ-56021927 (apalutamide) ARN-509-003 Documentation of Statistical Methods and Interim Analysis Plans

ARN-509-003 PRO Statistical Analysis Plan v2.0 26 June 2017

COPYRIGHT MATERIAL

Page 13 of 17

ARN-509-003 PRO Statistical Analysis Plan v2.0 26 June 2017

Page 14 of 17

COPYRIGHT MATERIAL

JNJ-56021927 (apalutamide) ARN-509-003 Documentation of Statistical Methods and Interim Analysis Plans

ARN-509-003 PRO Statistical Analysis Plan v2.0 26 June 2017 COPYRIGHT MATERIAL

Page 15 of 17

ARN-509-003 PRO Statistical Analysis Plan v2.0 26 June 2017

Page 16 of 17

